Continuous Glucose Monitoring System (CGMS): To evaluate the effect of blood glucose levels on eating behavior in a population of patients with diabetes in a free-living environment; we plan to study 15 lean healthy control subjects (BMI <25 kg/m²), 15 obese non-diabetic subjects (BMI > 30 kg/m²), 15 T2DM subjects who will be age and BMI-matched to obese, non-diabetic subjects, and 15 T1DM subjects who will be age and BMI matched to control, non-diabetic subjects. The participants will come to the research unit for a screening visit to review their medical history and receive a physical examination. Blood tests will be collected for exclusion of anemia (hematocrit), diabetes (A1c), untreated thyroid disease (TSH), or any other major health problems (liver enzymes and creatinine). The total amount of blood drawn will be less 1 table spoon. All female subjects will undergo a urine pregnancy test at the time of screening. These blood and urine tests will not be performed if they have been done within the 3 months prior to the screening visit. The participants who qualify will be invited to use the CGMS (DEXCOM G4 Platinum) for up to 7 days. On the visit for placement of the CGMS: 1) the participants will be explained by one of the study physicians how to use a glucometer (FreeStyle or Accu-Check), 2) they will have the CGMS inserted under the skin, and 3) they will be instructed how to fill up the food log (using informational brochures). On the second visit (up to 7 days after the initial visit) the CGMS will be removed from the skin and the glucose meter and food log will be returned to the investigators. The first visit will last approximately 1 hour and the second visit about 30 minutes. The CGMS consists of 3 parts: sensor, transmitter and monitor. The small sensor measures the glucose levels from the interstitial tissue. The transmitter is attached on top of the sensor and connects wirelessly to the monitor. The sensor is sterile and comes in an unopened package. It has a plastic wire-like tip that is placed under the skin and continuously measures the glucose levels. One of the study physicians will insert the CGMS wire-like tip under the volunteer's skin with the use of the DEXCOM sensor insertion kit. The transmitter is snapped to the sensor pod and the sensor/transmitter unit will be attached to the skin with an adhesive patch. The monitor is the size of a small hand-held device with a digital screen that displays a graph showing the glucose levels from the previous 4-24 hours. While using the CGMS, the volunteers will need to check their glucose levels with a glucose meter twice a day to calibrate the device. One of the investigators will teach the volunteers how to use the glucose meter, which will be loaned to the volunteers during the CGMS session. The monitor and transmitter should be kept 6 meters apart for adequate wireless communication. While using the CGMS the participants will be asked to fill up a food record. The Food Record will ask about amount and type of food consumed throughout the day. The participants will also register how hungry they are before the meal and how full they feel after they ate, and type and duration of physical activity. After completing the CGMS session, the sensor will be removed by one of the investigators. To remove the sensor, the adhesive patch will be gently peeled off from the skin, together with the sensor pod and transmitter. Removal of the sensor is a painless procedure. The sensor and sensor

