
pod will be discarded after use. The transmitter and receiver and glucose meter will be disinfected with a bleach solution and 70% isopropyl alcohol wipes to remove any disinfectant residue.

4. Genetic Testing N/A

A. Describe

- i. the types of future research to be conducted using the materials, specifying if immortalization of cell lines, whole exome or genome sequencing, genome wide association studies, or animal studies are planned
- ii. the plan for the collection of material or the conditions under which material will be received
- iii. the types of information about the donor/individual contributors that will be entered into a database
- iv. the methods to uphold confidentiality

B. What are the conditions or procedures for sharing of materials and/or distributing for future research projects?

C. Is widespread sharing of materials planned?

D. When and under what conditions will materials be stripped of all identifiers?

E. Can donor-subjects withdraw their materials at any time, and/or withdraw the identifiers that connect them to their materials?

- i. How will requests to withdraw materials be handled (e.g., material no longer identified: that is, anonymized) or material destroyed?

F. Describe the provisions for protection of participant privacy

G. Describe the methods for the security of storage and sharing of materials

5. Subject Population: Provide a detailed description of the types of human subjects who will be recruited into this study.

15 lean, healthy control subjects (BMI <25 kg/m²)

15 obese, non diabetic subjects (BMI > 30 kg/m²)

15 T2DM subjects who will be age and BMI-matched to obese, non-diabetic subjects

15 T1DM subjects who will be age and BMI matched to control, non-diabetic subjects.

6. Subject classification: Check off all classifications of subjects that will be specifically recruited for enrollment in the research project. Will subjects who may require additional safeguards or other considerations be enrolled in the study? If so, identify the population of subjects requiring special safeguards and provide a justification for their involvement.

 Children	 Healthy	 Fetal material, placenta, or dead fetus
 Non-English Speaking	 Prisoners	 Economically disadvantaged persons

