 Decisionally Impaired	 Employees	 Pregnant women and/or fetuses
 Yale Students	 Females of childbearing potential	

NOTE: Is this research proposal designed to enroll children who are wards of the state as potential subjects? Yes No (If yes, see Instructions section VII #4 for further requirements)

7. Inclusion/Exclusion Criteria: What are the criteria used to determine subject inclusion or exclusion?

Inclusion criteria (for both diabetic and non-diabetic participants):

- Age 18-65 years
- A1c < 10.5 %

Exclusion criteria:

BMI <18 (no upper limit), Creatinine > 1.5 mg/dL, Hgb < 10 mg/dL, ALT > 2.5 X ULN, untreated thyroid disease, uncontrolled hypertension, known neurological disorders, untreated psychiatric disorders, use of antidepressants and psychiatric medications, use of weight loss medications in the 6 months prior to the study, malignancy, smoking, current or recent steroid use in last 3 months, history of current illicit drug use; for women: pregnancy, or breastfeeding.

8. How will **eligibility be determined, and by whom?**

Eligibility will be determined by a qualified physician associated with the research protocol and will be based upon the above inclusion/exclusion criteria

9. Risks: Describe the reasonably foreseeable risks, including risks to subject privacy, discomforts, or inconveniences associated with subjects participating in the research.

The CGMS poses no major risks to the subjects. Participants may feel a mild discomfort (pin prick sensation) during the sensor insertion. Some individuals may experience black and blueness of the skin at the insertion site of the CGMS sensor, which resolves by itself in a few days. Redness and discomfort (inflammation) can occur at the sensor insertion site. Rarely sensors may fracture and a small piece may remain under the skin which will need to be removed by the physician. This may cause mild discomfort, bruising, or temporary bleeding.

Blood samples will be obtained with a needle inserted into a vein which results in mild discomfort, bruising and temporary bleeding.

10. Minimizing Risks: Describe the manner in which the above-mentioned risks will be minimized.

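### Does drawing A1c to exclude diabetes contradict a study in which half the participants are meant to have diabetes?

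*Combined protocol and SAP*

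**What the plan says.** Section V, item 3 (Research Plan) introduces the monitoring study as one "in a population of patients with diabetes in a free-living environment" and, in the same sentence, lists four groups of 15: lean healthy controls, obese people without diabetes, people with T2DM and people with T1DM. The next sentence begins "The participants will come to the research unit for a screening visit", with no group singled out. Blood is then drawn "for exclusion of anemia (hematocrit), diabetes (A1c), untreated thyroid disease (TSH), or any other major health problems (liver enzymes and creatinine"), again with no group named.

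Item 5 (Subject Population) repeats the four groups. Among them are "15 obese, non diabetic subjects" and "15 T1DM subjects who will be age and BMI matched to control, non-diabetic subjects".

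Item 7 opens with "Inclusion criteria (for both diabetic and non-diabetic participants") and gives two criteria: an age range of 18 to 65 and A1c below 10.5%. Its exclusion list contains "Creatinine > 1.5 mg/dL, Hgb < 10 mg/dL, ALT > 2.5 X ULN, untreated thyroid disease" and further conditions, but neither diabetes nor a second A1c limit. Item 8 says that the eligibility decision "will be based upon the above inclusion/exclusion criteria".

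Section VII, item 1 gives the enrolment target as 60.

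**The concern.** Two things look wrong. First, the screening sentence follows a statement about participants in general and uses A1c to rule out diabetes. Applied as written, it would remove the two groups that the study needs for its diabetes comparisons.

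Second, the criteria on which item 8 rests eligibility contain no such exclusion. The other four blood tests in the sentence (hematocrit, TSH, liver enzymes, creatinine) each lead to a recognisable exclusion in item 7. A1c leads only to a ceiling that is the same for people with and without diabetes. Someone auditing a control participant's file against item 7 alone would find nothing requiring that person to be free of diabetes.

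If this led to wrong enrolment, participants with diabetes could enter the lean or obese control groups. The contrast between diabetic and non-diabetic glucose profiles would then be blurred.

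**Working it through.** The arithmetic is limited to counts.

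- Planned enrolment: 15 + 15 + 15 + 15 = 60, which reproduces the target in Section VII, item 1.
- Meant to have diabetes: 15 (T2DM) + 15 (T1DM) = 30, and 30/60 = 50%.
- Left under a literal reading of the screening sentence: 60 − 30 = 30, the lean and obese groups only.

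The question is whether a reader of the plan could reach that literal result, or could admit a control with diabetes. Setting the items side by side answers it.

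**Where each kind of criterion is kept**

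| Feature | Item 7 (common to all) | Items 3 and 5 (by group) |
|---|---|---|
| BMI | Exclude below 18; no upper limit | Lean below 25; obese above 30; T1DM and T2DM groups matched on BMI |
| Type of diabetes | Not mentioned | T1DM group; T2DM group |
| Freedom from diabetes | Not mentioned | Lean controls healthy; obese group non-diabetic; T1DM matching line calls the controls non-diabetic |
| A1c | Below 10.5% | Drawn to exclude diabetes (item 3) |

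The BMI row is the useful comparison. Item 7 alone would admit a person with a BMI of 27, who fits neither the lean group (below 25) nor the obese group (above 30). Nobody would take that as permission to enrol that person as a lean control, because the group limits are in items 3 and 5. A1c follows the same pattern: an outer limit for everyone in item 7, and group status elsewhere. Item 7 also never requires a T1DM or T2DM participant to have that diagnosis. The absence of a non-diabetic criterion is therefore part of how the plan is laid out and is not peculiar to A1c.

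**Whether the literal reading is available**

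The four groups are named in the sentence immediately before the screening visit is introduced. A test to exclude diabetes can apply only to the two groups described as healthy or non-diabetic; in the other two, diabetes is the condition for entry. The item 7 heading also takes it for granted that both kinds of participant are enrolled.

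**Whether a control with diabetes could slip through**

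Every participant has an A1c result, either drawn at screening or available from the preceding 3 months. Medical history is reviewed at the same visit. For patients found through clinic appointments, Section VII, item 6 adds a check of the diabetes diagnosis before the first call. A qualified physician makes the eligibility decision under item 8. The information needed to place each person in the right group is collected, and the stated purpose of the A1c test tells the physician how to use it.

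**Effect on the figures**

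The power statement in item 12 rests on 15 per group and differences in standard deviation units. Neither depends on how the A1c sentence is worded.

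**The case for a change.** The strongest case for acting is that item 8 ties eligibility to the listed criteria, and nowhere does the plan say what result makes a person non-diabetic. The lean group is called healthy, and becomes non-diabetic only through the T1DM matching line. A label does not tell a screener how to treat a raised A1c in someone with no known diagnosis, and a review of recorded diagnoses would miss exactly that person. Naming the groups and stating the sponsor's own definition would take about two lines, with no new test or visit.

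Part of this stands. The screening sentence lacks its qualifier, no definition of non-diabetic is written down, and a strict reading of item 8 sends the reader to a list that does not separate the groups. It does not follow that undiagnosed diabetes goes unaddressed: the sentence at issue is the one that says A1c is drawn to rule diabetes out. Recognising diabetes from an A1c result is routine for a study physician.

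The counts add little. The 30 of 60 are affected only under a reading that the rest of the paragraph rules out. That one test in five lacks a matching exclusion is true only if the item 7 A1c ceiling is set aside because it is listed under inclusion.

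**Conclusion.** The observation about the wording is accurate, but it does not show a fault in the design. Items 3, 5 and 7 can be read together in only one sensible way: A1c excludes diabetes from the lean and obese groups, and the 10.5% ceiling applies to everyone. Anything added would write down what the plan already means, so this is a clerical gap that the study physician fills and no change follows.

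Its size is one missing qualifier and one unwritten definition. The effect on estimates, power and sample size is nil on the evidence in the protocol.

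This rests on two assumptions: that eligibility is judged from the whole plan and not from item 7 in isolation, and that the physician applies an ordinary clinical understanding of non-diabetic to the control groups. The documents give no reason to doubt either.

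### The 3-month carry-over of screening tests includes the urine pregnancy test, so a woman can be enrolled without a current test although pregnancy is an exclusion

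*Combined protocol and SAP*

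**What the plan says.** The screening visit is described in Section V, item 3 (Research Plan) of the combined protocol and SAP. Blood is taken for hematocrit, A1c, TSH, liver enzymes and creatinine. On pregnancy the text reads: "All female subjects will undergo a urine pregnancy test at the time of screening". The next sentence is the waiver: "These blood and urine tests will not be performed if they have been done within the 3 months prior to the screening visit".

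Section V, item 7 (Inclusion/Exclusion Criteria) admits "Age 18-65 years" and lists among the exclusions "for women: pregnancy, or breastfeeding".

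Two other provisions bear on the point. At screening, participants also come to "review their medical history and receive a physical examination" (item 3). Item 8 says: "Eligibility will be determined by a qualified physician associated with the research protocol", on the basis of the listed criteria.

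**The concern.** A carry-over of 3 months is a defensible choice for the blood tests. A pregnancy test is different in kind: a negative result describes the day it was taken and says nothing about conception afterwards. By naming urine tests, the waiver removes the current test for some of the women whom the preceding sentence says will all be tested.

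What is at stake is whether a stated exclusion is backed by current evidence. A site that follows the waiver exactly can record a woman as not pregnant on an old result and be fully compliant. The protocol chose to check this exclusion with a test, so the waiver weakens a safeguard that the protocol itself put in place.

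**Working it through.** No sample-size or power figure underlies this point. The check compares the provisions and adds some date arithmetic.

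**1. Does the waiver reach the pregnancy test?** The waiver covers blood and urine tests. The only urine test named in the document is the pregnancy test. If the waiver did not cover it, the word for urine would refer to nothing. On the plain text, the waiver covers it.

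**2. Whom does it affect?**

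| Woman at screening | Sentence on the pregnancy test | Waiver sentence | Result |
|---|---|---|---|
| No pregnancy test in the previous 3 months | Test | Does not apply | Tested at screening |
| Pregnancy test in the previous 3 months | Test | Test not performed | Enters on the earlier result |

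Only the second row is affected. The age range in item 7 includes women who can become pregnant.

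**3. How old can the result be?** Three calendar months span 89 to 92 days. The window is counted back from the screening visit. Let g be the number of days from screening to sensor placement, which the protocol does not state.

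- At screening: up to 89 to 92 days.
- At sensor placement: up to 89 to 92 + g days.
- At the end of a full 7-day wear: up to 89 + 7 = 96 to 92 + 7 = 99 days, plus g.

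Even with g = 0, the result can be 3 months old at entry.

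**4. Does another provision close the gap?**

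- The placement visit in item 3 lists three activities: glucometer teaching, sensor insertion and food-log instruction. None is a pregnancy test.
- Item 7 has no contraception criterion and sets no shorter window for this test.
- Section VIII only lists the pregnancy test among the laboratory data collected.
- History, examination and the eligibility decision apply to every participant. They can detect a known or clinically evident pregnancy, but cannot be relied on for one the woman has not recognised.

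No provision requires a repeat test.

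**5. Can the effect be sized?** No. The protocol gives no expected number of women, no proportion with a recent test and no probability of conception since that test. It also does not say that pregnancy changes glucose, hunger or food intake.

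**The case against.** **The two sentences are a rule and an exception.** A reader might call them a flat contradiction. They can be carried out as written: test every woman unless she was tested recently. This stands. The difficulty is that the exception undercuts the exclusion that the rule serves.

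**The exclusion still operates.** A reader might infer that it fails altogether for women who enter under the waiver. The documents do not support that. Pregnancy excludes in its own right, whatever a test shows, and history, examination and physician review remain. What is lost is detection of an unrecognised pregnancy that began after the earlier test.

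**The exposure is narrow.** It needs a test in the previous 3 months, a conception since, and a pregnancy missed on history and examination. This stands too, and it limits the severity.

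**Bias in the results.** A reader might reason that one woman is 1/15 = 6.7% of a group, so that a deviation of 2 to 3 SD would move the group mean by 2/15 = 0.13 to 3/15 = 0.20 SD. The arithmetic is right, but the deviation is an assumption with no source in the protocol. Item 12 (Statistical Considerations) gives detectable differences of 1.0 to 1.25 SD, so even that shift is 0.13/1.25 = about 11% to 0.20/1.0 = 20% of them. The stated aim is also how glucose profiles relate to hunger and intake, for which a shift in a group mean is not the direct measure of harm.

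**Safety.** A reader might infer a hazard to a pregnant participant. The risks in item 9 concern sensor insertion and blood sampling, and none is specific to pregnancy.

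**The unticked box for females of childbearing potential in item 6.** This does not answer the point. The box marks groups specifically recruited and does not exclude such women; the protocol provides for testing all female subjects.

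**Conclusion.** The point holds as a gap in eligibility checking. As written, the waiver lets a woman satisfy the pregnancy exclusion on a negative result up to 3 months old at screening, and older by an unstated interval at sensor placement. No other provision requires a current test.

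This rests on reading the waiver's reference to urine tests as meaning the one urine test named, and on the fact that a negative test cannot exclude a later conception. It does not rest on any effect of pregnancy on the study's measures. Such an effect is plausible because glucose, hunger and intake are what the study records, but it is an inference. The number of women affected and any bias cannot be computed from the documents. Severity is minor to moderate.

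**What to change.** Reconcile the waiver in Section V, item 3 with the sentence before it and with the pregnancy exclusion in item 7. The simplest way is to limit the 3-month carry-over to the blood tests, so that the screening pregnancy test already in the plan applies to all female subjects. The age of the result at sensor placement would then fall from as much as 89 to 92 + g days to g days. That still leaves g open, so the protocol should also state the interval from screening to placement.

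If the sponsor does intend the carry-over to include the pregnancy test, the protocol should say so and explain how the exclusion is then verified.

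The cost is a one-sentence amendment and one urine test for each woman who would otherwise be waived, at a visit already scheduled.

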Furthermore, previous published data from our lab¹³, subjects using a 2-step clamp, i.e. euglycemia (~90 mg/dL) followed by mild hypoglycemia (~65 mg/dL) in conjunction with fMRI and visual stimuli of food/non-food, showed that euglycemia was associated with activation of prefrontal cortex (PFC) and anterior cingulate ($p < 0.05$), while during hypoglycemia there was activation of hypothalamus, nucleus accumbens, insula, caudate and putamen in response to visual food cues ($p < 0.05$). In addition, hunger was increased during hypoglycemia as compared to the euglycemic phase (5.7 ± 0.5 vs 4.5 ± 0.5 ; $p < 0.01$). The study also included a small group of obese subjects ($n=5$). When this group was compared to lean subjects, they failed to show activation of the medial pre-frontal cortex during euglycemia and showed greater bilateral activation of the hypothalamus, striatum and insula in response to high-calorie food images during mild hypoglycemia ($p < 0.05$). Taken together the data suggest that during euglycemic phase of the clamp study there was activation of PFC in lean individuals, a region involved in complex cognitive behaviors, decision making and moderating correct social behavior¹⁴, whereas during hypoglycemic phase limbic regions were activated; which are involved in physiological and emotional responses¹⁵. Of particular interest these preliminary data suggest that the neural response to food consumption and food cues is altered in obese individuals in a way that could contribute to overeating behavior, namely increased stimulation of reward centers in response to nutrients (glucose) and/or food cues. This differentiated brain response could be a contributing factor to the pathogenesis of human obesity. We also plan to study patients with diabetes, who have chronic high glucose levels. Preliminary work from our group showed that obese unlike lean subjects suppressed activity in the ventral medial PFC (executive-control area) in response to food images; with a preferential liking/wanting for high-calorie food during hyperglycemia¹⁶. Therefore, we want to investigate if changes in circulating glucose levels can interfere with eating behavior and food intake in lean, obese subjects and patients with diabetes.

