Continuous glucose monitoring (CGM) is used in people with diabetes for better glycemic control as well as in non-diabetic individuals to characterize glucose patterns¹⁷⁻¹⁹. No study thus far has looked into glucose profiles normal weight, obese, and diabetic individuals in a normal, outpatient setting in relation to hunger and food intake. In a preliminary study of 8 individuals who wore a CGMS for 1 week and recorded their food intake and hunger levels, we found that increasing subjective hunger levels are more related to pre-prandial glucose peaks as opposed to nadirs. Furthermore, declines in glucose are correlated with caloric intake as well as the

macronutrient content of subsequent meals. Our findings suggest that glycemic excursions following a meal may play a role in hunger and food choices for the subsequent meal.

3. Research Plan: Summarize the study design and research procedures using non-technical language that can be readily understood by someone outside the discipline. Be sure to distinguish between standard of care vs. research procedures when applicable, and include any flowcharts of visits specifying their individual times and lengths. Describe the setting in which the research will take place.

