This is a pilot project. We estimate that a sample size of 15 subjects per group will provide 80% power to detect within group differences of 1.1 standard deviations. For changes in hunger ratings of liking, wanting and hunger we will have at least 80% power to detect between group differences across all glycemic conditions (i.e. main effect of group) of 1.0 standard deviation and within each condition of 1.25 standard deviations.

SECTION VI: RESEARCH INVOLVING DRUGS, BIOLOGICS, RADIOTRACERS, PLACEBOS AND DEVICES

N/A

A. DRUGS, BIOLOGICS and RADIOTRACERS

1. **Identification of Drug, Biologic or Radiotracer:** What is (are) the **name(s)** of the drug(s) biologic(s) or radiotracer(s) being used? Identify whether FDA approval has been granted and for what indication(s).

All protocols which utilize a drug, biologic or radiotracer **not** approved by, but regulated by, the FDA, or a radiotracer regulated by the RDRC, must provide the following information:

- a. What is the Investigational New Drug (IND) **number** assigned by the FDA?
- b. Who holds the IND?
- c. All protocols which utilize a radiotracer not approved by, but regulated by the FDA must provide the IND number: _____
Alternatively, use of the investigational radiotracer may be under RDRC/RSC oversight: (check if appropriate) _____

For all investigational radiotracers, attach a copy of the RDRC/RSC application (for radioisotopes used in the PET Center, PET Center personnel may complete this step)
Go to <http://rsc.med.yale.edu/login.asp?url=myApps.asp>. When you have logged in, complete the application and attach a copy to this submission.

Alternatively, an **exemption from IND filing requirements** may be sought for a clinical investigation of a drug product that is lawfully marketed in the United States. If there is no IND and an exemption is being sought, review the following categories and complete the category that applies (*and delete the inapplicable categories*):

Exempt Category 1

The clinical investigation of a drug product that is lawfully marketed in the United States can be exempt from IND regulations if all of the following are yes:

- i. The intention of the investigation is NOT to report to the FDA as a well-controlled study in support of a new indication for use or to be used to support any other significant change in the labeling for the drug. Yes No

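### As described, the food record does not show whether food was eaten to treat or prevent low glucose, so the glucose-intake association in T1DM may mix appetite with glucose self-management

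*Combined protocol and SAP*

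**What the plan says.** Section V, item 3 (Research Plan) sets the aim for this part of the work: "To evaluate the effect of blood glucose levels on eating behavior in a population of patients with diabetes in a free-living environment". The groups include "15 T1DM subjects who will be age and BMI matched to control, non-diabetic subjects".

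On the food log, the same item says: "The Food Record will ask about amount and type of food consumed throughout the day". Participants also "register how hungry they are before the meal and how full they feel after they ate, and type and duration of physical activity". Every participant carries a monitor with a "digital screen that displays a graph showing the glucose levels from the previous 4-24 hours", so anyone can eat in response to a reading.

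The reason for eating is not mentioned anywhere. Section VIII, item a lists medications among the health information collected, without time or dose. Section V, item 7 does not exclude users of glucose-lowering drugs. Section V, item 12 (Statistical Considerations) names no analysis for episodes eaten to manage glucose.

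**The concern.** A person at risk of low glucose may eat because they are hungry, because glucose is low, or because they expect it to fall. The described record cannot tell these apart. Food eaten to manage glucose would tend to be small and high in carbohydrate, and would be taken when glucose is low or near normal. In the T1DM group this steepens the association between lower glucose and higher carbohydrate share, even if appetite responds to glucose exactly as it does in lean controls. The difference could then be read as altered eating behavior in T1DM. Intent cannot be reliably reconstructed once the week of wear is over.

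This is a problem of separating two pathways, not of confounding. Eating at a low is partly the effect of glucose on eating that the study wants to measure. The Background reports from an earlier clamp study that "hunger was increased during hypoglycemia as compared to the euglycemic phase" (5.7 against 4.5). For the same reason, a high hunger rating does not show that an episode was appetite-driven.

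**Working it through.** The plan gives no figure on this point to reproduce.

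**1. What the existing data can recover.** Assume 10% of T1DM episodes are self-management, with a strong food contrast (defined in step 2) and no true glucose-carbohydrate association.
- If these episodes occur at about 62 mg/dL, dropping readings below 70 mg/dL takes the within-person correlation in T1DM from -0.36 to -0.06.
- If they are preventive, at about 85 mg/dL, the same cut moves it from -0.30 to -0.34, so nothing is repaired.

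Flagging small, high-carbohydrate episodes instead would select on the outcome.

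**2. Inputs for size.** The 15 per group is from the plan; everything else is assumed.
- 28 episodes per person.
- Ordinary glucose: T1DM 160 (SD 55, floored at 45) mg/dL; lean 92 (SD 12) mg/dL.
- Carbohydrate share of ordinary episodes: 48% (SD 12).
- Preventive episodes, T1DM only: glucose 85 (SD 8) mg/dL; carbohydrate share 90% (strong contrast) or 70% (weak), SD 8.
- Shared true slope b: -0.033 or -0.15 points of carbohydrate share per mg/dL, with no between-person variation.

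**3. Expected T1DM slope.** With a share f of preventive episodes, and ignoring the floor:

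slope = [(1-f)·b·V + f(1-f)·Δg·Δc] / [(1-f)·V + f·Vp + f(1-f)·Δg²]

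Here V = 55² = 3025, Vp = 8² = 64, Δg = 85 - 160 = -75, and Δc = 90 - 48 = 42 (strong) or 70 - 48 = 22 (weak).

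For f = 0.10 and b = -0.033:
- Denominator: 2722.5 + 6.4 + 506.3 = 3235.2.
- Strong: (-89.8 - 283.5)/3235.2 = -0.115.
- Weak: (-89.8 - 148.5)/3235.2 = -0.074.

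The same formula gives -0.078 and -0.055 at f = 0.05, and -0.175 and -0.103 at f = 0.20.

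**4. Effect of marking.** If 80% of preventive episodes are marked and dropped, the remaining share is f' = 0.2f/(1-0.8f), that is 0.010, 0.022 and 0.048. Put into the formula with the strong contrast, these give -0.043, -0.053 and -0.076.

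**5. Simulation.** Slopes are for b = -0.033. The false-difference range covers both contrasts and both shared slopes, using a Welch t test on per-person slopes.

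| Preventive share | T1DM slope | Slope with 80% marked, strong contrast | False T1DM-lean difference, p<0.05 |
|---|---|---|---|
| 0% | -0.033 | -0.033 | about 5% |
| 5% | -0.06 to -0.08 | -0.04 | 7-12% |
| 10% | -0.08 to -0.12 | -0.055 | 7-31% |
| 20% | -0.11 to -0.18 | -0.08 | 9-75% |

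The simulated slopes agree with steps 3 and 4. The low ends of the last column are hardly above the nominal 5%.

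**6. Why slopes and not correlations.** With carbohydrate SD 12 in both groups, an equal correlation of -0.15 means a slope of -0.15 × 12/55 = -0.033 in T1DM but -0.15 × 12/12 = -0.15 in lean participants. The lean response is then 55/12 = 4.6 times as strong, so equal correlation is not equal response. Conversely, with a shared slope and no self-management episodes at all, a test comparing correlations already rejects in about 38% (slope -0.033) to 100% (slope -0.15) of simulated studies.

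**The case against.** **The gap is inferred from a summary.** Item 3 is written in non-technical language, and the log and brochures are not supplied. Clock time of eating is not listed either, though pre-prandial analyses need it. This stands as a limit: the point concerns the record as described. Eating times differ, however, in that the preliminary analysis in the Background already depends on them. Nothing in the plan implies a field for reason.

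**Free-living eating is the target.** Eating at a low is part of what glucose does to eating, and CGM can largely identify it. This stands, and it is why no episode should leave the main analysis. What remains is mainly preventive eating, of unknown frequency, chiefly in 15 of 60 participants in a self-described pilot.

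**The comparison is not explicitly planned.** A reader might infer from "we will have at least 80% power to detect between group differences across all glycemic conditions" that item 12 commits the study to comparing glucose-intake associations between groups. It does not: that sentence concerns ratings of liking, wanting and hunger. The concern rests instead on the stated aim and on matching T1DM participants to lean controls.

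**A larger effect is tempting.** A reader who compares correlations might infer that a false group difference is close to certain at a 20% share. That does not follow, because the different glucose spread alone separates the correlations (step 6), and no log item repairs that.

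**Other outcomes are less affected.** The Background's preliminary result is that "declines in glucose are correlated with caloric intake". For glucose declines the effect is zero if self-management episodes do not follow larger declines. For hunger it is smaller and of unknown sign.

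**Conclusion.** The point holds for the record as described. It cannot separate appetite from glucose self-management in T1DM participants, or in T2DM participants whose drugs can cause low glucose (their treatment is not stated). CGM covers much of the eating at measured lows but not preventive eating near normal glucose.

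The size is uncertain. Under the stated assumptions, a true slope of -0.033 is inflated to between -0.06 and -0.18. The false-difference rate runs from near nominal to 75%, depending on the share of preventive episodes and on how different the food is. With no between-person variation in slope simulated, the rates are on the high side. Imperfect marking still helps: at a 20% share with strong contrast, 80% marking cuts the shift from 0.142 (0.175 - 0.033) to about 0.047 (0.08 - 0.033), removing about two-thirds.

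Two further inferences are not supported. The documents do not show that the T1DM data would be uninterpretable. Nor do they show that drug time and dose must be logged to resolve this: dosing is a possible common cause, but a mealtime dose can be chosen for the planned meal, and it does not record why food was eaten.

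This is a worthwhile improvement to make before logs are issued, not a reason to hold the study.

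**What to change.** 1. Add one item per eating episode to all 60 logs: *Eaten mainly to treat a low glucose / to prevent a low glucose / neither*. Treating and preventing stay separate, and the prompt is the same in every group. If the log already has such a field, say so in item 3.
2. Keep all episodes in the main analysis.
3. Pre-specify one sensitivity analysis in item 12 that repeats the glucose-intake and glucose-hunger analyses without the marked episodes. Report both estimates side by side, with the share marked in each group.
4. Where groups are compared on these associations, use within-person slopes per mg/dL, not correlations.

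Recording drug time and dose is optional and not needed for this fix.

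The cost is one extra log item, a small recording burden and one additional analysis. Self-report will be incomplete. The sensitivity analysis also loses part of the low-glucose range and part of a real glucose effect, so it should not replace the main analysis. This is data capture only; nobody's treatment changes.
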